## 5. TREATMENT OF SUBJECTS

### 5.1 Investigational product/treatment

Patients will be randomly assigned to receive either the fasting mimicking diet, the food supplement or the placebo.

The FMD arm will follow 3 cycles of the diet for 3 consecutive months. One cycle consists of 5 continuous days of the diet followed by 25 days of normal food intake.

Patients in the food supplement and placebo arm will receive 4 capsules per day, for 3 consecutive months. The food supplement and placebo arm will be double blinded.

Patients in the supplement group (placebo or food supplement) will be instructed to not change their diet during the study.

### 5.2 Use of co-intervention

Patients included in the study can be on standard diabetic care consisting of oral hypoglycemic drugs or insulin. During the study, the diabetes medication will/can be altered, which is explained in paragraph 5.3. Included patients can also be on standard antihypertensive care with antihypertensive medication. The antihypertensive drugs can be altered during the study and is left to the discretion of the investigator. However, preferably RAAS inhibitors will not be altered during the study as this can influence heparanase activity and albuminuria.

Other co-medication is allowed with the exception of immunosuppressive (such as prednisolone) and low molecular weight heparin. Use of co-medication should be documented.

### 5.3 Glucose monitoring

#### Endocalyx and placebo group

Patients are asked at baseline if they ever experienced hypoglycemia. The symptoms of hypoglycemia are explained at baseline and glucose monitoring will be done at the end of every month (T2, T3 and T4). Patients that use rapid acting insulin are instructed to track glucose levels during one day (before every meal and before going to bed in the evening) in the week prior to the study visit. At the study visit, fasting glucose will be measured with a finger prick blood sample. Patients are asked if they experienced hypoglycemia during the last month. If the fasting glucose at the study visit is between 4.0 and 15.0 mmol/L and the patient did not experience hypoglycemia during that month, the dosage (for that patient) of hypoglycemic drugs is not altered. However, if the patient did experience hypoglycemia during that month or the measured fasting glucose at the study visit is below 4.0 mmol/L, the dosage of hypoglycemic drugs will be altered according to the investigators opinion.

### FMD group

Patients that use sulfonylureas or insulin will be provided with a glucose meter and strips at baseline. The device and strips will be provided for free. These patients will get an instruction from the investigator or research staff on how to self-measure glucose levels.

Patients are asked at baseline if they have ever experienced hypoglycemia. The symptoms of hypoglycemia are explained and provided in a patient letter to patients that use sulfonylureas or insulin. The patient letter contains a telephone number and instructions on what to do if the patient experiences symptoms of hypoglycemia or if the self-measured glucose drops below 4.0 mmol/L. Patients are instructed to call the investigator if they experienced hypoglycemia during weekdays and the internal resident on duty at the Haaglanden Medical Center in the evening/night of weekdays and on weekend days.

Treatment of hypoglycemia will be performed according to the investigator's or physician's decision and the guidelines of hypoglycemia. The dosages of the hypoglycemic medication can be adjusted if needed.

[figure not shown]
To prevent hypoglycemia during the diet, the dosages of oral hypoglycemic drugs and insulin will be altered during the 5 days of the diet. These alterations are shown in flow chart II.

Sulfonylurea's and rapid acting insulin will be stopped, and the dosage of long acting insulin will be halved during the 5 days of the diet. The sulfonylurea drugs will be stopped one day prior to the start of the diet. Metformin will be continued during the diet. Patients that still use long actin insulin during the diet are asked to measure fasting glucose levels during the 5 days and track glucose levels 4 times throughout the second day of the diet. These patients will be contacted by the investigator during the diet to monitor the glucose levels.

Patients will return to their normal dosage of oral hypoglycemic drugs or insulin for the next 25 days of the month. Patients that return to sulfonylureas or long- or rapid acting insulin are instructed to measure the fasting glucose for the first 3 days after the diet. The investigator or one of the research staff will contact these patients by phone in the first following days after returning to their normal diet.

At the end of every month, the previous FMD cycle is evaluated together with the glucose monitoring, by measuring fasting glucose levels with a finger prick blood sample. Patients that use rapid acting insulin are instructed to track glucose levels during one day (before every meal and before going to bed in the evening) in the week prior to the study visit. If the fasting glucose at the study visit is between 4.0 and 15.0 mmol/L and the patient did not experience hypoglycemia during that month, the dosage (for that patient) of hypoglycemic drugs is not altered. However, if the patient did experience hypoglycemia during that month or the measured fasting glucose at the study visit is below 4.0 mmol/L, the dosage of hypoglycemic drugs will be altered according to the investigators opinion.

Flow chart II: Hypoglycaemic drug dosage adjustment during the 5-day FMD

#### 5.4 Escape medication

Treatment of hypoglycemia will be performed according to the investigator's or physician's decision and the guidelines of hypoglycemia. In case of an allergic reaction to one of the ingredients of the diet or food supplement, standard treatment with anti-histamines will be given. Severe cases of allergic reaction will be treated with epinephrine, prednisolone and evaluated in the hospital.

## 6. INVESTIGATIONAL PRODUCT

### 6.1 Name and description of investigational products

#### 6.1.1 Fasting Mimicking diet: Prolon™

The fasting mimicking diet that will be used in this study is called Prolon™ (further termed Prolon), produced by L-Nutra. Prolon is a 5 day plant-based, low caloric, low protein, diet that is designed for humans to attain water fasting like effects while minimalizing the burden of fasting.

#### 6.1.2 Food supplement: Endocalyx™

Endocalyx™ (further termed Endocalyx) is a food supplement distributed by Microvascular Health Solutions. The supplement combines three complementary and synergistic working mechanisms to support the endothelial glycocalyx function, by supplying sulfated polysaccharides, anti-oxidant enzymes, and additional substrates for glycocalyx synthesis.

#### 6.1.3 Placebo

The placebo will be produced by the pharmacy of the LUMC and will mimic the Endocalyx capsules.

## 6.2 Summary of findings from non-clinical studies

### 6.2.1 Fasting mimicking diet

Dietary restrictions such as intermitting fasting in non-clinical studies established beneficial effects on oxidative damage, inflammation and life span by inducing metabolic and cellular changes [44]. Fasting improved glucose and insulin sensitivity, reduced circulating inflammatory markers and insulin-like growth factor 1 (IGF-1) serum levels, a hormone associated with aging and cancer, and induced autophagy, which is impaired in diabetic nephropathy and contributes to glomerular inflammation and endothelial dysfunction [37, 43, 45].

The metabolic effects of the FMD were observed in non-diabetic and type 2 diabetic mice. In non-diabetic mice, a 4-day fasting mimicking diet twice a month reduced glucose and IGF-1 levels majorly at the end of the fasting cycle compared to the control group, whereas ketone bodies increased by 9 fold. These markers, however, returned to baseline levels within the days of refeeding [38]. In diabetic mice, alternate day fasting reversed high insulin and glucose levels to normal levels, despite similar overall food intake compared to the control group [46]. This was also seen in db/db mice, which develop insulin resistance in early stages and beta cell failure in later stages. Weekly cycles of a 4-day FMD reduced fasting glucose levels to nearly normal levels and improved glucose tolerance and insulin levels, which led to an overall better survival [37].

The fasting mimicking diet also obtained anti-inflammatory effects. In the db/db mice, inflammatory cytokines such as TNF-alpha, IL-12, and MCP-1 were suppressed after multiple FMD cycles [37]. In C57BL/6 mice, prone to develop malignant lymphomas, inflammation in lymph nodes and the liver was reduced after multiple 4-day FMD cycles, with reduced tumour incidence and delayed onset of the disease [38].

Another interesting effect of fasting mimicking diets was the induction of beta cell regeneration in healthy and T1D human pancreatic islets by reducing IGF-1 levels and downregulating mTOR and PKA signalling [37]. Inhibition of the mTOR pathway causes an upregulation of autophagy, which is impaired in diabetic nephropathy. Others also showed that intermitting fasting or calorie restriction in rats with diabetic nephropathy obtained anti-inflammatory effects and upregulated autophagy by increasing SIRT1 expression in the kidney [47, 48]. The mTOR and SIRT1 pathways are important nutrient-sensing pathways and regulators of autophagy [49].

### 6.2.2 Food supplement

Administration of the Endocalyx supplement in a mouse model of aging revealed anti-inflammatory and beneficial vascular effects. In old mice, the food supplement increased arterial nitric oxide production by 50%, decreased mesenteric macrophage accumulation by 60%, lowered blood pressure by 25%, increased capillary density by 50%. These effects led to an improvement in microvascular health index compared to baseline (unpublished data, [name]).

## 6.3 Summary of findings from clinical studies

### 6.3.1 Fasting mimicking diet

The Longo group developed Prolon, a plant based low-protein low-caloric 5-day fasting mimicking diet for humans. This intermitting short period of fasting obtains the beneficial effects on IGF-1, inflammation, glucose and insulin levels similar of water fasting, while providing micronutrients to minimize the burden of fasting.

In a pilot study, 19 healthy volunteers followed this diet for 5 days per month for 3 consecutive months. At the end of the first 5-day cycle, fasting glucose, IGF-1 levels and body weight were significantly reduced and these effects remained after resuming a normal diet, one week after finishing the third cycle. As a marker for systemic inflammation and risk factor for cardiovascular disease, C-reactive protein levels were measured. For subjects with CRP levels in the moderate to high risk range at baseline, levels returned within the normal range after 3 FMD cycles [38].

After that, a larger randomized cross over trial with the Prolon diet was conducted with 71

healthy individuals that completed 3 cycles of the diet in 3 months. A significant reduction in BMI, total body fat, systolic blood pressure, and serum IGF-1, total cholesterol, HDL and LDL levels was seen one week after finishing the third FMD cycle. A post hoc analysis that stratified the effects of the diet by risk factor showed that only for subjects with prediabetic fasting glucose levels ( $>99$  mg/dL) and for subjects with high CRP levels ( $>1.0$  mg/L) at baseline, levels returned to normal ranges 5 days after finishing the third FMD cycle. Moreover, a voluntary follow-up 3 months after finishing the third FMD cycle showed that the significant beneficial effects on body weight and inflammation remained in all follow-up subjects. For subjects with at-risk levels at baseline, fasting glucose, IGF-1 levels and the systolic blood pressure were still significantly reduced 3 months after finishing the last FMD cycle, indicating that the beneficial effects of the diet may last for several months [39]. In conclusion, the fasting mimicking diet has a long lasting positive effect on metabolic factors but also obtains anti-inflammatory effects in subjects with a high cardiovascular risk profile.

### 6.3.2 Food supplement

A pilot study was conducted among 13 healthy volunteers receiving the Endocalyx food supplement. After 3 months, the Microvascular Health Index measured by SDF imaging improved by 31%. After 4 months, the Microvascular Health Index in the volunteers improved by 50%. This showed the beneficial effects of the food supplement on the microvasculature as it significantly increased capillary density and red blood cell filling percentage, and reduced the perfused boundary region (unpublished data, [name]).

## 6.4 Summary of known and potential risks and benefits

### 6.4.1 Fasting mimicking diet

A low caloric, low energetic diet such as the Prolon diet can give discomfort and symptoms such as hunger, fatigue, dizziness, muscle aches, headaches and possible fainting. In the study with 71 healthy subjects following diet, no severe or life threatening adverse effects were reported. The most reported adverse effects were mild fatigue (45%), weakness (35%), headache (30%), dry mouth (18%), memory impairment (18%) and muscle pains (10%) [39]. The pilot study with 19 healthy subjects also did not report any severe or life threatening adverse effects of the FMD [38]. Another possible side effect may be an unknown allergic reaction to one of the ingredients of the diet.

Because of the low caloric intake during the 5 days of the diet, adequate measurements are taken to prevent hypoglycemia during the diet as illustrated in 3.2 and flow chart II. Benefits of the diet are improvements in metabolic factors such as body weight, blood pressure, triglycerides, insulin sensitivity and fasting glucose. For patients with diabetic

nephropathy, benefits remain to be established but are potentially substantial with a reduction in albuminuria by decreasing systemic and glomerular inflammation burden which may improve the glomerular microvascular health.

#### 6.4.2 Food supplement

In the pilot study with Endocalyx, no serious adverse effects were reported. One side effect that was reported was dizziness, as the endocalyx supplement lowered the systolic blood pressure. The supplement is already used in general practitioners offices in the United States and to date; no one reported any major side effects. Studies conducted with the individual ingredients also did not report any serious adverse effects, this is further explained in the structured risk analysis (paragraph 12). A possible side effect may be an unknown allergic reaction to one of the ingredients of the supplement.

Benefits of the Endocalyx food supplement in diabetic patients remain to be established but are mainly improving the microvascular health by supporting endothelial glycocalyx function.

### 6.5 Description and justification of route of administration and dosage

#### 6.5.1 Fasting mimicking diet

The Prolon diet will be provided in a box where each day is separately packaged. The box consists of plant-based soups, bars, drinks, snacks, herbal teas, vitamins, and supplements. A specific combination of food is provided on each day for breakfast, lunch, dinner and snacks. The diet consists of a 5 day regime with day 1 providing 1,090 kcal (10% protein, 56% fat, and 34% complex carbohydrate), whereas days 2 to 5 provide 725 kcal (9% protein, 44% fat, and 47% complex carbohydrate) per day. The Prolon diet is lactose and gluten free but contains nuts, soy and tomato as ingredients. Water and herbal tea can be consumed without a limit during the 5 days of the diet. The characteristics of the diet are the lack of refined carbohydrate, very low protein content and high levels of healthy fats from plant based sources.

#### 6.5.2 Food supplement

##### Composition of one Endocalyx capsule

Ingredient	Amount (mg/capsule)
Fucoidan (85%)	106.25 mg
Oxxyne OMD-MVHS Blend SOD (Superoxide dismutase, catalase and polyphenols)	120.00 mg
Glucosamine Sulfate	375.00 mg
Hyaluronic Acid 1800-3000 kDa	17.50 mg
Microcrystalline Cellulose	130.00 mg
Silicon Dioxide	2.00 mg
Total mg per capsule	750.75 mg

Fucoidan is a fucosylated and sulfated polysaccharide extracted from the brown algae species *Laminaria japonica* that mimics heparan sulfate, the main glycosaminoglycan of the endothelial glycocalyx.

Hyaluronan or hyaluronic acid is also a glycosaminoglycan that is incorporated in the endothelial glycocalyx.

Oxynea OMD-MVHS Blend SOD contains superoxide dismutase (SOD) and polyphenolic enzymes extracted from olive, grape and artichoke. These enzymes act as antioxidants, capable of helping to prevent cellular and molecular damage caused by free radicals, such as reactive oxygen species, through scavenging the oxidants and inhibiting further activity.

Glucosamine sulfate is extracted from corn, and is an amino sugar and precursor in the biochemical synthesis of glycosylated proteins and lipids. It can increase synthesis of two main constituents of the endothelial glycocalyx, namely heparan sulfate and hyaluronan.

Silicon dioxide and microcrystalline cellulose are natural anti-caking agents used to prevent the components from sticking together.

### **6.5.3 Placebo**

The placebo capsule will mimic the Endocalyx capsules and will consist of microcrystalline cellulose and silicon dioxide.

## **6.6 Dosages, dosage modifications and method of administration**

### **6.6.1 Fasting mimicking diet**

One FDM cycle consist of 5 continuous days of the Prolon diet followed by 25 days of normal food intake. Patients will follow 3 cycles for 3 consecutive months.

### **6.6.2 Food supplement**

Patients will receive 4 capsules Endocalyx per day, in total 3 grams per day, for 3 consecutive months. The capsules are orally administered and can be taken with water, on an empty stomach or with food.

### **6.6.3 Placebo**

Patients will receive 4 capsules of the placebo per day for 3 consecutive months. The capsules are orally administered and can be taken with water, on an empty stomach or with food.

## **6.7 Preparation and labelling of Investigational Medicinal Product**

### **6.7.1 Fasting mimicking diet**

Prolon will be produced and distributed by L-Nutra, a company based in Los Angeles, California. Prolon contains only plant-based, natural food components generally regarded as safe (GRAS, US Food and Drug Administration label).

### **6.7.2 Food supplement**

Endocalyx is a food supplement that is distributed by Microvascular Health Solutions LLC in Alpine, Utah. Preparation and labelling of the Endocalyx is done according to the relevant good manufacturing practice (GMP) guidelines by CSB Nutrition Corporation. The food supplement will be re-labelled, blinded and distributed by the LUMC pharmacy.

### **6.7.3 Placebo**

Preparation and labelling of the placebo is done according to the relevant good manufacturing practice (GMP) guidelines by the pharmacy of the LUMC. The placebo will be blinded and distributed by the pharmacy of the LUMC.

## **6.8 Drug accountability**

### **6.8.1 Fasting mimicking diet**

The Prolon boxes will be stored in the LUMC. The principal investigator is responsible for providing the Prolon box to the patients before the start of every cycle and is responsible for checking the expiration date on the packages in the boxes.

### **6.8.2 Food supplement**

The supplements will be stored in the pharmacy of the LUMC. CSB nutrition is responsible for verifying if the supplements meet the release criteria. The investigator is responsible for providing the supplements to the patients at baseline and at the end of the first and second month.

### **6.8.3 Placebo**

The placebo will be stored in the pharmacy of the LUMC. The pharmacy is responsible for verifying if the placebo meets the release criteria. The investigator is responsible for providing the placebo to the patients at baseline and at the end of the first and second month.

## 7. METHODS

### 7.1 Study parameters/endpoints

#### 7.1.1 Main study parameter/endpoints

The primary endpoint is to improve the endothelial microvascular health expressed by an improvement in Microvascular Health Index between baseline and 3 months of treatment in South Asian patients with type 2 diabetes mellitus through:

1. The fasting mimicking diet in comparison to the placebo.
2. The endocalyx food supplement in comparison to the placebo.

#### 7.1.2 Secondary study parameters/endpoints

Secondary endpoints include;

- Albuminuria: urinary excretion of albumin, using albumin/creatinine ratio in mg/mmol.
- Inflammation: urinary heparanase and MCP-1 expression, serum C-reactive protein, and MCP-1 levels.
- Metabolic response: fasting glucose, HbA1c, C-peptide, IGF-1, total cholesterol, LDL cholesterol, HDL cholesterol, triglycerides levels, body weight, waist circumference, waist-to-hip ratio and systolic blood pressure.
- Identifying specific urinary heparan sulfate domains.

To evaluate the legacy effects of the interventions, the primary and secondary parameters will also be assed three months after stopping the intervention.

#### 7.1.3 Other study parameters

Urinary ketones are measured after the first 5 days of the first FMD cycle to determine the compliance of the patients in the diet group.

ASAT and ALAT are measured for monitoring liver function, serum creatinine level for monitoring kidney function and the frequency of hypoglycemia during the study is documented as safety endpoints.

### 7.2 Randomisation, blinding and treatment allocation

Eligible patients will be randomized during the run in period into the FMD, food supplement or placebo arm after given informed consent. Randomisation will be performed by the LUMC pharmacy. The placebo and food supplement group will be double blinded. The pharmacy will store the randomization code. The investigator or pharmacy can deblind the subjects in the occurrence of any AE, SAE, or abnormality in a laboratory assessment which, in the opinion of the investigator, warrants the subject's permanent withdrawal from the trial.

Patient specific data will be stored under a subject identification code and randomization number for each patient. There will be a subject identification code list that links the codes to a subject. This list will be stored for 15 years by the principal investigator. Data will be presented for the complete intention-to-treat population as well as the per protocol population.

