**Intervention:** One group receives a monthly 5-day fasting mimicking diet, one group receives daily 4 capsules of a food supplement and one group receives daily 4 placebo capsules, all for 3 consecutive months.

**Main study parameters:** The primary endpoint is an improvement of the Microvascular Health index in the diet group compared to the placebo group and in the food supplement group compared to the placebo group, after 3 months of the intervention.

Secondary endpoints: reduce albuminuria, decrease inflammation (urinary heparanase and MCP-1 expression, serum CRP and MCP-1 levels), reduce occurrence of specific urinary HS domains, improve metabolic parameters; fasting glucose, HbA1c, C-peptide, IGF-1, total cholesterol, LDL cholesterol, HDL cholesterol, and triglycerides serum levels, waist circumference, waist-to-hip ratio, body weight and systolic blood pressure after 3 months of the fasting mimicking diet and after 3 months of the food supplement.

The legacy effect of the interventions is also determined, 3 months after stopping with the intervention.

**Nature and extent of the burden and risks associated with participation, benefit and group relatedness:** Eligible patients are randomly assigned to the fasting mimicking diet, food supplement or placebo arm. At baseline, after 3 months and at 6 months, the MHI is measured by non-invasive SDF imaging of the microcirculation under the tongue, and blood and urine samples are collected. In the FMD arm, dosages of the hypoglycemic drugs are adapted during the 5 days of the diet prevent hypoglycemia. Glucose monitoring is done during the diet and at the end of each month in all intervention arms through a finger prick blood sample.

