### 3. STUDY DESIGN

A 6-month, single center randomized controlled trial to study the effects of dietary interventions on improving endothelial health in South Asian patients with diabetic nephropathy. In total 90 South Asian patients with type 2 diabetes and proven microalbuminuria between 18-75 years of age will be recruited at general practitioner centers in the The Hague region. Eligible patients will be included for a period of 6 months. Patients will be randomly assigned to receive the fasting mimicking diet, food supplement or placebo for a period of 3 months. The primary endpoint is an improvement of the Microvascular Health index after 3 months in the diet group compared to the placebo group and in the food supplement group compared to the placebo group, measured with SDF-imaging. After 6 months, which is 3 months after stopping with the interventions, patients will also return for a follow-up measurement to investigate possible legacy effects of each intervention.

The food supplement and placebo arm will be double blinded. The placebo arm will also be used as a control group for the FMD arm.

Study procedures will take place at the practice of the general practitioner and will be performed by LUMC research staff. The general practitioner will not perform any of the study procedures. Flow chart I gives an overview of the study design and time points for study visits.

Flow chart I

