### **SDF imaging**

Sidestream dark field (SDF) imaging is a non-invasive technique that measures the endothelial glycocalyx with a handheld camera that visualizes the sublingual microvasculature. The CE-marked camera is put under the tongue of the patients and measures in total about 3000 vascular segments in the sublingual vessels. The investigator moves the camera to a different location in the mouth until the total amount of frames necessary is determined automatically. This takes about 2-4 minutes.

The camera uses green LED light to detect the hemoglobin in red blood cells and measures lateral red blood cell (RBC) movements, RBC filling percentage, vessel density, and local vascular perfusion efficiency. These parameters reflect the endothelial glycocalyx health status and are affected if the glycocalyx layer is impaired [32, 33]. The image acquisition is automatically mediated through the Glycocheck software (Glycocheck BV, Maastricht, the Netherlands), which combines these parameters and calculates the Microvascular Health Index (MHI). This index ranges from 0.00 to 10.00 with a score between 0.00 – 1.00 reflecting a clinically perturbed glycocalyx and perfusion in the microvasculature, a score between 1.00 – 2.00 a less than average health of the microvasculature, 2.00 – 3.00 an average microvascular health, between 3.00 and 5.00 an above average and a score above 5.00 a good functional microcirculation with adequate endothelial glycocalyx coverage and flow mediated adaptation.

In addition, capillary tortuosity will be determined by placing the SDF camera in four quadrants of the inner lip (duration about 1-2 minutes): the upper right quadrant, upper left quadrant, lower right quadrant and lower left quadrant. From these collected frames, the

capillary tortuosity will be assessed by scoring the number of twists per capillary in the capillaries in the field of view per image. The number of twists will be stratified as 0: no twists (or pinhead capillaries) to 4: four or more twists, described by Djaberi et al. [53] The overall tortuosity score per subject will be determined by selecting the most frequent tortuosity score in the 12 studied microcirculatory imaging areas (3 microcirculatory imaging areas per quadrant).

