## 9. STATISTICAL ANALYSIS

### 9.1 Primary study parameter

SPSS will be used for all statistical analysis. Data analysis will be performed based on the intention to treat principle. Patients will be included in the analyses according to the treatment to which they were randomised.

The primary endpoint Microvascular Health index (MHI) will be summarized in mean with standard deviation or median with interquartile range. The effect within the group between baseline and 3 months is tested using a paired Student's t test (two-tailed). Differences in improvement of the MHI between baseline and 3 months between the FMD group and the placebo group and the food supplement and placebo group will be tested with an independent Student's t test.

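### Randomisation precedes the T0 baseline MHI and the plan does not withhold the arm until T0 is done, so the open FMD arm's change score is exposed to bias at its starting point

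*Combined protocol and SAP*

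**What the plan says.** **Order of events.** Section 7.2: "Eligible patients will be randomized during the run in period into the FMD, food supplement or placebo arm after given informed consent". The pharmacy performs the randomisation and holds the code; no time is given for releasing the arm to staff or patient. The schedule in section 7.3 has a run-in column ahead of T0. The Summary fixes when the outcome is recorded: "At baseline, after 3 months and at 6 months, the MHI is measured by non-invasive SDF imaging".

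**Blinding.** Section 3: "The food supplement and placebo arm will be double blinded", and "The placebo arm will also be used as a control group for the FMD arm". No section blinds FMD patients, the SDF operator or an outcome assessor.

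**What happens at baseline.** In the FMD part of section 5.3: "Patients that use sulfonylureas or insulin will be provided with a glucose meter and strips at baseline". Section 6.8 has capsules handed out at baseline and diet boxes before each cycle. Section 5.1 tells only the capsule groups to keep their diet unchanged.

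**Measurement.** Section 7.3, SDF imaging: "The investigator moves the camera to a different location in the mouth until the total amount of frames necessary is determined automatically". Also: "The image acquisition is automatically mediated through the Glycocheck software", and that software computes the index.

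**Analysis.** Section 9.1 compares, by independent t test, "Differences in improvement of the MHI between baseline and 3 months between the FMD group and the placebo group", and likewise supplement with placebo. No baseline adjustment is mentioned. The same section commits to analysing patients in the arm to which they were randomised.

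**The concern.** A change score is safe from allocation effects at its starting point only if the baseline is taken before anyone concerned knows the arm. Here the stated sequence is the reverse, and one of the two active arms is open.

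Two routes could move the FMD baseline. The operator places the camera by hand and could be influenced by knowing the arm. A patient who knows that a diet is coming could eat differently before T0; this would also touch baseline weight, fasting glucose and lipids, which are secondary endpoints. FMD versus placebo is one of the two primary comparisons, so a shift at T0 would enter a headline result.

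There is also a gap in the analysis set. A patient randomised in the run-in who leaves before T0 has no baseline MHI and so no change score. Section 7.6 provides no study follow-up after withdrawal, section 7.5 allows some drop-outs to be replaced, and no rule says how such a patient is kept in an analysis by randomised arm.

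**Working it through.** **1. Inputs.** From section 4.4: difference in improvement 0.35, SD 0.41, two-sided alpha 0.05, 23 evaluable per group, 25% drop-out, 30 enrolled per group. From section 9.1: two-sample t test on change. The baseline shift b is not in the documents; the values 0.05, 0.10 and 0.15 are assumptions.

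**2. The plan's own figure.** With standardised difference 0.35 / 0.41 = 0.854, the exact (noncentral t) calculation needs 22.5, so 23 per group, with power 80.8%. The stated 23 is reproduced. For drop-out, 23 / 0.75 = 30.7 against 30 enrolled; the gap is trivial and not at issue.

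**3. How a shift enters the estimate.** Write Y0 and Y3 for MHI at T0 and 3 months. The contrast is mean(Y3 − Y0) in FMD minus mean(Y3 − Y0) in placebo. If the mean FMD Y0 is too low by b and nothing else changes, the contrast rises by exactly b; if too high by b, it falls by b. Adjusting for baseline would not cure this, because the covariate is itself measured after allocation: the bias becomes slope × b rather than b.

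**4. Size.** SE of the contrast = 0.41 × √(2/23) = 0.121, with 2 × 23 − 2 = 44 degrees of freedom.
- Type I error: probability that a noncentral t with noncentrality b / SE exceeds the two-sided 5% limits, with no true effect.
- Power when the shift works against the diet: the same calculation with noncentrality (0.35 − b) / SE, upper limit.

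| Assumed b | b / 0.35 | b / SE | Type I error, FMD baseline too low | of which favours FMD | (0.35 − b) / SE | Power, FMD baseline too high |
|---|---|---|---|---|---|---|
| 0 | 0% | 0 | 5.0% | 2.5% | 2.89 | 80.8% |
| 0.05 | 14% | 0.41 | 6.9% | 6.0% | 2.48 | 68.0% |
| 0.10 | 29% | 0.83 | 12.8% | 12.5% | 2.07 | 52.5% |
| 0.15 | 43% | 1.24 | 22.9% | 22.8% | 1.65 | 36.6% |

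More patients do not remove the problem. With 30 evaluable per arm and b = 0.10, the type I error is 15.3%; with the opposite sign, power is 64.2% instead of 90.2%.

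**5. When could the arm be known?** Section 5.3 ties meters and instruction to baseline for FMD patients on certain drugs, and has sulfonylureas stopped the day before the diet begins. The first-cycle ketone check falls on diet day 5 and the T1 visit on day 4–5, so the diet starts at about T0. Disclosure at or shortly before T0 is therefore plausible, but no section states when it happens or that imaging comes first.

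**The case against.** The strongest reply is that the plan is silent on disclosure, and silence is not evidence that anyone knows the arm at T0. The meters and instructions could be handed over after the imaging at the same visit, and the pharmacy could hold the allocation until then. A reader might infer that staff already hold the allocation when they record T0; the documents do not establish that. What stands is that nothing in the plan prevents it, while the stated order of randomisation and baseline makes it possible.

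A reader might also infer a gap of up to 30 days between randomisation and T0. That figure comes only from a column header. Section 7.2 gives no interval, and the marks in the schedule cannot be read reliably in the extracted text, so I place no weight on them.

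On measurement, about 3000 vascular segments are recorded, the software decides when enough frames have been taken, and it calculates the MHI. Patients also attend without having eaten or smoked that morning. This limits operator influence considerably. It does not remove it, since the site is chosen by hand, and it does nothing about changed eating in the days before.

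On direction, the table should not be read as predicting false positives. Altered eating before T0, if it did anything, might raise the FMD baseline and work against the diet. Both signs have to be shown.

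Finally, a reader might suppose that losses before T0 would be heavier in the diet arm. No section supports that, and no figure is given for losses before T0 in any arm.

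**Conclusion.** The point holds as an avoidable risk of bias in the FMD-versus-placebo comparison. It is not shown that bias will occur. It rests on three things the plan does state: randomisation in the run-in before the T0 MHI, blinding of the capsule arms only, and an unadjusted change-score test. It also rests on one omission: no step withholds the arm until T0 is complete.

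The one-for-one transfer of a shift follows from the change score. The sizes in the table are illustrations: they assume a constant shift in the FMD mean at T0, an unaffected 3-month value and an unchanged SD of 0.41, and nothing in the documents says that shifts of 0.05 to 0.15 are likely. The supplement-versus-placebo comparison is largely protected by its double blinding. The missing change score for anyone lost before T0 is a real gap against section 9.1, of unknown size. Overall this is a cheap and worthwhile improvement; the sample size is unaffected.

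**What to change.** Amend section 7.2 and the section 7.3 schedule so that randomisation, or at the least release of the arm to staff and patient, takes place only after every T0 measurement is complete: SDF imaging, blood, urine, anthropometry and questionnaires. Define a patient as randomised from that moment, so that anyone lost during the run-in falls outside the randomised set and everyone inside it has had the T0 assessment. The pharmacy can still prepare the list and the stock in advance.

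The cost is protocol wording and a small logistic burden: diet boxes and capsules must both be available at T0 or delivered just after it. The baseline instructions in section 5.3, including those that apply before the first diet day, have to be reconciled with the new release point; how is for the clinical team.

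The change protects only the T0 half of the contrast. The FMD arm remains open at 3 months, and the plan does not blind the operator there; that needs separate treatment.
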